Endpoint	
Primary endpoint: weight (lb),
 
Secondary endpoint: hemoglobin A1c levels, BMI, steps per day, diagnosis of diabetes, engagement score based on dDPP data logs and lesson completions, and patient demographics, social determinants, and other baseline descriptive data

Study Duration	
Phase 2: 18 Months
 
Phase 3: 42 Months

Participant Duration	
18 months

Duration of behavioral intervention	
12 months

CONFIDENTIAL

This material is the property of the NYU School of Medicine and NYU Langone Health. Do not disclose or use except as authorized in writing by the study sponsor Behavioral Intervention Template Version: 11 January 2019

Population	Pre-diabetic adult patients at NYU Langone Health (phase 2 and phase 3) and providers for the pre-diabetic patients (phase 2)
Study Sites	NYU Langone Health Faculty Group Practice (FGP), NYU Langone Family Health Center (FHC)
Number of participants	Phase 2: 40 patient participants and 40 provider participants          Phase 3: 433 participants and 20-40 provider participants.

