#### 4.2.2 Secondary Study Endpoints

Secondary endpoint: steps per day, hemoglobin A1c levels, diagnosis of diabetes, engagement score based on dDPP data logs and lesson completions, and patient demographics, social determinants, and other baseline descriptive data

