## **5.2 Exclusion Criteria**

An individual who meets any of the following criteria will be excluded from participation in this study:

Provider Exclusion Criteria: Refuse to participate

Patient Exclusion criteria:

An individual who meets any of the following criteria will be excluded from participation in this study:

1. Diagnosed with diabetes
2. Patients whose weight may vary considerably over the study's timeframe for reasons other than the intervention (e.g. cancer, pregnancy, ascites, severe CHF)
3. Patients with severe psychiatric disease or dementia
4. Active health condition that prevents them from engaging in moderate exercise

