## **5.7 Participant Withdrawal or Termination**

### **5.7.1 Reasons for Withdrawal or Termination**

Participants are free to withdraw from participation in the study at any time upon request. An investigator may terminate participation in the study if:

- Any clinical adverse event (AE), laboratory abnormality, or other medical condition or situation occurs such that continued participation in the study would not be in the best interest of the participant
- The participant meets an exclusion criterion (either newly developed or not previously recognized) that precludes further study participation

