### **5.7.2 Handling of Participant Withdrawals or Termination**

Participants will be referred to the investigator for evaluation and management. Data collection will cease at the time of withdrawal. Data up until the point of withdrawal will be used in the analysis.

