### **7.3.5 Withdrawal Visit**

In the event that involuntary withdrawal data collection will cease at the time of withdrawal. Data up until the point of withdrawal will be used in the analysis.

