## 8.3 Time Period and Frequency for Event Assessment and Follow-Up

The occurrence of an AE or SAE may come to the attention of study personnel during study visits and interviews of a study participant presenting for medical care, or upon review by a study monitor. All AEs including local and systemic reactions not meeting the criteria for SAEs will be captured on the appropriate RF. Information to be collected includes event description, time of onset, clinician's assessment of severity, relationship to study intervention (assessed only by those with the training and authority to make a diagnosis), and time of resolution/stabilization of the event. All AEs occurring while on study must be documented appropriately regardless of relationship. All AEs will be followed to adequate resolution.

Any medical condition that is present at the time that the participant is screened will be considered as baseline and not reported as an AE. However, if the study participant's condition deteriorates at any time during the study, it will be recorded as an AE. UPs will be recorded in the data collection system throughout the study.

Changes in the severity of an AE will be documented to allow an assessment of the duration of the event at each level of severity to be performed. AEs characterized as intermittent require documentation of onset and duration of each episode.

The PI will record all reportable events with start dates occurring any time after informed consent is obtained until 7 (for non-serious AEs) or 30 days (for SAEs) after the last day of study participation. At each study visit, the investigator will inquire about the occurrence of AE/SAEs since the last visit. Events will be followed for outcome information until resolution or stabilization.

All unresolved adverse events should be followed by the investigator until the events are resolved, the subject is lost to follow-up, or the adverse event is otherwise explained. At the last scheduled visit, the investigator should instruct each subject to report any subsequent event(s) that the subject, or the subject's personal physician, believes might reasonably be related to participation in this study. The investigator should notify the study sponsor of any death or adverse event occurring at any time after a subject has discontinued or terminated study participation that may reasonably be related to this study.

CONFIDENTIAL

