### **13.5 Participant and Data Confidentiality**

Information about study subjects will be kept confidential and managed according to the requirements of the Health Insurance Portability and Accountability Act of 1996 (HIPAA). Those regulations require a signed subject authorization informing the subject of the following:

- What protected health information (PHI) will be collected from subjects in this study
- Who will have access to that information and why
- Who will use or disclose that information
- The rights of a research subject to revoke their authorization for use of their PHI.

In the event that a subject revokes authorization to collect or use PHI, the investigator, by regulation, retains the ability to use all information collected prior to the revocation of subject authorization. For subjects that have revoked authorization to collect or use PHI, attempts should be made to obtain permission to collect at least vital status (i.e. that the subject is alive) at the end of their scheduled study period.

Participant confidentiality is strictly held in trust by the participating investigators, their staff, and the sponsor(s) and their agents. This confidentiality is extended to cover testing of biological samples and genetic tests in addition to the clinical information relating to participants. Therefore, the study protocol, documentation, data, and all other information generated will be held in strict confidence. No information concerning the study or the data will be released to any unauthorized third party without prior written approval of the sponsor.

The study monitor, other authorized representatives of the sponsor, or representatives of the IRB may inspect all documents and records required to be maintained by the investigator, including but not limited to, medical records (office, clinic, or hospital) and pharmacy records for the participants in this study. The clinical study site will permit access to such records.

The study participant's contact information will be securely stored at each clinical site for internal use during the study. At the end of the study, all records will continue to be kept in a secure location for as long a period as dictated by local IRB and Institutional regulations.

Study participant research data, which is for purposes of statistical analysis and scientific reporting, will be transmitted to and stored at the NYU Langone research drive. The study data entry and study

CONFIDENTIAL

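### A new diabetes diagnosis is both a secondary endpoint and a permitted ground for ending follow-up, so month-12 weight and HbA1c can be lost because an outcome occurred

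*Combined protocol and SAP*

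**What the plan says.** - **Endpoint.** Section 4.2.2 lists as secondary endpoints "steps per day, hemoglobin A1c levels, diagnosis of diabetes, engagement score based on dDPP data logs and lesson completions". The Protocol Summary also includes it: "hemoglobin A1c levels, BMI, steps per day, diagnosis of diabetes".
- **Exclusion.** The first patient exclusion criterion in section 5.2 is "Diagnosed with diabetes".
- **Termination.** Section 5.7.1 says an investigator may end participation if "The participant meets an exclusion criterion (either newly developed or not previously recognized) that precludes further study participation".
- **Consequence.** Section 5.7.2, whose heading covers both withdrawal and termination, states: "Data collection will cease at the time of withdrawal. Data up until the point of withdrawal will be used in the analysis". Section 7.3.5 says: "In the event that involuntary withdrawal data collection will cease at the time of withdrawal".
- **What continues after exit.** Section 8.3 asks the investigator to notify the sponsor of "any death or adverse event occurring at any time after a subject has discontinued or terminated study participation" if it may reasonably be related to the study. Section 13.5 says that after revoked authorization "attempts should be made to obtain permission to collect at least vital status". Neither covers weight or HbA1c.
- **Analysis.** Section 10.3 sets an intention-to-treat dataset of everyone randomized. Section 10.4.2 plans weighted GEE under a missing-at-random assumption and EHR extraction to fill missing weight and HbA1c. It does not list the covariates of the weight model or say whether extraction continues after termination.

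**The concern.** An intention-to-treat comparison needs follow-up that does not depend on the outcome. Here the stated rules let follow-up stop because of one. The trial enrols people with prediabetes and a baseline self-test HbA1c of up to 6.4, so some new diagnoses during the year are to be expected. If those patients also tend to lose less weight, removing them makes the remaining patients in their arm look better than the arm really did. If the arms differ in how many such patients are removed, the treatment difference shifts.

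At stake are the month-12 weight (the primary endpoint) and month-12 HbA1c (a secondary endpoint) of patients diagnosed before month 12. The decision to terminate is left to judgement, and section 10.6.1 says neither patients nor providers are blinded. No section says that the investigator who decides is blinded.

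**Working it through.** **1. The plan's own figures.** The documents give no figure for this bias. The nearest stated quantity is power in section 10.5 (SD 5 kg, two-sided 0.05), calculated as Φ(d / (5√(2/n)) − 1.96):

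- 2 kg, 200 per arm: Φ(4.00 − 1.96) = 97.9% (stated 97%)
- 1.75 kg, 200 per arm: Φ(3.50 − 1.96) = 93.8% (stated 93%)
- 2 kg, 160 per arm: Φ(3.58 − 1.96) = 94.7% (stated 94%)

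These reproduce to within a point. The same SD with 144 per arm gives the yardstick used below: 5√(2/144) = 0.59 kg.

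**2. A check that needs no HbA1c cut-off.** Let pC and pT be the shares removed in the control and intervention arms, and let removed patients do worse than their arm mean by an excess e. The shift in the month-12 difference among those retained is e × [pC/(1 − pC) − pT/(1 − pT)]. With pC = 5% and pT = 2% the bracket is 0.0526 − 0.0204 = 0.0322. For e of 1 to 4 kg (assumed), the shift is 0.03 to 0.13 kg toward no effect. Swapping the two shares gives the same amount away from it.

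**3. Simulation.** From the plan: a 2 kg effect, SD 5 kg, 144 per arm, and baseline HbA1c of 5.4 to 6.4. Assumed:

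- baseline HbA1c mean 5.8 or 5.9, SD 0.25, truncated to the inclusion range
- HbA1c change SD 0.2 or 0.3, with half of that variance persistent
- HbA1c effect −0.10
- correlation between weight change and HbA1c change 0.3 or 0.5, either at the same visit or in the stable component
- month-6 HbA1c above 6.4 as a stand-in for diagnosis (the documents do not equate the two)
- the same treatment effect at months 6 and 12

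This gives about 4 to 13 stand-in diagnoses per 144 control patients and 2 to 8 per 144 in an intervention arm.

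The month-12-only contrast is not the planned estimator. Section 10.4.2 plans a repeated-measures GEE with time and intervention effects, and section 5.7.2 keeps data gathered before exit. With months 6 and 12 in the model, an independence working correlation and no weights, the intervention coefficient averages an intact month-6 contrast and a shifted month-12 contrast with nearly equal weight. The shift is therefore about halved.

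| Share of diagnosed removed (control / intervention) | Month-12-only shift, kg | Time-plus-intervention model, kg | Direction |
|---|---|---|---|
| 100% / 100% | 0.02–0.13 | 0.01–0.06 | toward null |
| 75% / 25% | 0.02–0.21 | 0.01–0.10 | toward null |
| 25% / 75% | 0.00–0.09 | 0.00–0.04 | away from null |
| 0% / 100% | 0.02–0.24 | 0.01–0.12 | away from null |

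The direction reverses once the intervention removal share is about 1.4 to 2.0 times the control share. For HbA1c, the month-12-only shift is 2–8%, 3–13%, 0.5–5% and 2–14% of the assumed 0.10 effect, in the same row order and directions.

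**4. Weights.** With inverse-probability weights on arm and on month-6 HbA1c above or below 6.4, partial removal leaves at most about 0.003 kg in the month-12 contrast. If every diagnosed patient is removed, nobody of that type remains to be weighted up.

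**5. Harsher inputs.** For the month-12-only contrast, 10% against 5% diagnosed and removed, with a 5 kg gap between removed and retained patients in each arm, gives 5 × 0.05 = 0.25 kg. 15% against 8% gives 5 × 0.07 = 0.35 kg. Both need a gap of a full SD.

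**The case against.** **Termination is optional.** Section 5.7.1 says may, and it applies only to an exclusion criterion that precludes further participation. That wording implies that some criteria do not. Listing diabetes as an endpoint fits with following those patients. This stands: a reader might infer that the protocol requires diagnosed patients to be removed, and it does not. But no section says that a new diabetes diagnosis falls outside the rule, and section 5.2 bars anyone meeting a listed criterion from participating. An investigator could reasonably read it either way.

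**The planned analysis absorbs much of the bias.** This also stands. The repeated-measures model about halves the month-12 figures under independence. Under an exchangeable correlation of 0.75 (assumed), every pattern fell within about 0.03 kg of zero. The plan does not name the working correlation. An intervention-by-time interaction, which sections 10.4.9 and 10.4.10 leave open, would make this dilution smaller.

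**EHR extraction may fill the gap.** It may. A patient terminated for diabetes has not revoked authorization, and nothing expressly forbids extraction. Nothing says that it continues either, and the rule that collection ceases reads against it.

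**Unequal detection through the dashboard.** Only intervention patients' providers have the dashboard, so a reader might infer that diabetes would be found more readily in those arms. The documents do not support this. Section 10.4.2 names weight and activity data as viewable and sources HbA1c from the home kit, survey and EHR. The in-app outcomes mentioned in section 6.1 are not said to include HbA1c. Beyond the lack of blinding, there is no textual basis for expecting removal to differ by arm.

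**Conclusion.** The point holds as a permitted, not a mandatory, outcome-dependent loss of follow-up. Under the assumptions above and the planned model without weights, the bias in the weight difference is roughly 0.01 to 0.12 kg with either sign, about a fifth of the 0.59 kg standard error at most (0.12/0.59 = 0.20). A month-12-only contrast reaches about 0.24 kg, still under half of it. Suitable weights or continued EHR extraction would reduce this further. That the bias is small follows from the assumed ranges; the documents give no incidence, HbA1c SD or correlation.

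Two stronger readings should be resisted. A reader might infer that the trial loses its diabetes endpoint. It does not, because the diagnosis precedes the exit and data up to that point are kept. A reader might also infer a definite bias toward no effect. That follows if removal is equally likely in each arm and the tool suite works, but the documents fix neither condition. This is a cheap improvement to the protocol and does not threaten the primary conclusion.

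**What to change.** Add to the second bullet of section 5.7.1: *A new diagnosis of diabetes after randomization is a study endpoint and is not by itself a reason to end study follow-up; scheduled weight and HbA1c, including EHR values, are still collected through month 12 unless the participant withdraws consent.* Whether the patient keeps using the app or receiving messages can stay a clinical decision.

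The cost is one amendment sentence and continued follow-up of a few patients on the existing schedule, with no new visits or procedures. The downside is that values after diagnosis include the effect of any diabetes treatment started, which is consistent with the intention-to-treat analysis.

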### **5.7.2 Handling of Participant Withdrawals or Termination**

Participants will be referred to the investigator for evaluation and management. Data collection will cease at the time of withdrawal. Data up until the point of withdrawal will be used in the analysis.

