## **10.3 Analysis Datasets**

Our primary analyses will use intention-to-treat (ITT) analysis dataset of all randomized participants. Participant baseline demographics and clinical characteristics will be collected. Repeated measurements of participant weight, physical activity, and HbA1c level at baseline, 6 and 12 months from baseline, and patient engagement and perceived provider involvement at 6 and 12 months from baseline will also be collected. Long-formatted data will be stored and analyzed.

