#### 10.4.2 Analysis of the Primary Efficacy Endpoint(s)

The table below outlines the study's main outcomes. Whenever possible, outcomes ascertained via automated or technology-facilitated objective approaches are used to enhance the pragmatic approach and minimize provider and patient burden; while weight and activity data will be collected more frequently (and be viewable to intervention patients and providers), 6- and 12- month assessments will be used to evaluate impact. To ensure data endpoint capture for weight and physical activity at 6 and 12 months, the study team will conduct outreach and troubleshoot with patients missing data at any of these intervals.

Construct	Measure	Data Source	Collected at (months)
Clinical outcomes	Weight reduction (kg)	Noom via wireless scale and survey, EHR	Baseline, 3, 6, 9, 12
	Physical activity (steps/day)	Noom via wireless pedometer	Baseline, 6, 12
	Hemoglobin A1C (%)	HbA1C home test kit and survey, EHR	Baseline, 6, 12
Engagement outcomes	Patient engagement (# dDPP logins) (# dDPP lessons completed)	Noom	6, 12
	Perceived provider involvement with dDPP progress	Patient portal 1-item survey	
Patient characteristics	Demographics, social determinants, and other baseline descriptive data	EHR	Baseline, 12

Change in body weight, a repeatedly measured continuous variable, will be our primary weight-based outcome. Secondarily, we will assess achievement of a 7% weight loss (the DPP weight goal), a binary outcome. Weight will be collected from the bluetooth linked wireless weight scale (Fitbit Aria or iHealth Fit/Nexus) that automatically reports weigh-ins to the Noom server. Mean steps per day, a repeatedly measured continuous variable, will be assessed using Fitbit or iHealth accelerometers integrated into the Noom platform. This objective device has been well-validated for the measurement of steps and found to be acceptable by study participants. HbA1C, the most common test used for prediabetes monitoring, will be assessed as a secondary outcome via HbA1C testing performed at home. HbA1C will be collected at baseline, 6 and 12 months. Patients will be sent a HbA1C testing kit upon enrollment, and prompted by

CONFIDENTIAL

This material is the property of the NYU School of Medicine and NYU Langone Health. Do not disclose or use except as authorized in writing by the study sponsor Behavioral Intervention Template Version: 11 January 2019

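### All data collection stops at any withdrawal or termination, so obtainable 6- and 12-month weight and HbA1c may be lost, sometimes for outcome-related reasons

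*Combined protocol and SAP*

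**What the plan says.** Section 5.7.2, which covers both withdrawal and termination, states: "Data collection will cease at the time of withdrawal. Data up until the point of withdrawal will be used in the analysis." Section 7.3.5 applies the same rule to investigator-initiated exits: "involuntary withdrawal data collection will cease at the time of withdrawal." Neither section separates leaving the program or stopping study contact from refusing further use of data.

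Section 5.7.1 lets an investigator terminate participation for an adverse event, laboratory abnormality or other medical condition, or when "The participant meets an exclusion criterion (either newly developed or not previously recognized) that precludes further study participation." Exclusion 1 in section 5.2 is "Diagnosed with diabetes." Exclusion 2 covers patients whose weight may vary over the study "timeframe for reasons other than the intervention (e.g. cancer, pregnancy, ascites, severe CHF"). Section 4.2.2 lists among the secondary endpoints "steps per day, hemoglobin A1c levels, diagnosis of diabetes", and section 4.2.1 makes weight the primary endpoint.

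Section 10.3 states: "Our primary analyses will use intention-to-treat (ITT) analysis dataset of all randomized participants." Section 10.4.2 evaluates impact at 6 and 12 months, with weight sent automatically from a wireless scale. For gaps in weight and activity, "the study team will conduct outreach and troubleshoot with patients missing data at any of these intervals"; missing weight and HbA1c are to be supplemented from the EHR. Remaining gaps are handled by weighted GEE under a missing-at-random assumption, with no weight model given. Section 10.4.2 does not say whether the outreach or the EHR query continues after withdrawal or termination.

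**The concern.** An ITT comparison of all randomised participants needs outcomes on as many of them as possible, including those who stop the program. Read plainly, 5.7.2 ends collection for everyone who leaves, including a participant whose investigator ended participation and who would have agreed to further weights or an EHR look-up.

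Some of this loss may be related to outcome. A participant who develops diabetes has reached a secondary endpoint and also meets exclusion 1. A participant with a new weight-changing condition meets exclusion 2, where the trial's primary variable is weight. No section exempts either criterion after randomisation. The patients remain in the ITT set, so the problem is missing values within it rather than exclusion from it.

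The 12-month contrast can then be biased in either direction. Better HbA1c on intervention would mean more losses in control. But the trial is unblinded (10.6.1) and only intervention-arm providers have the dashboard (6.1), so detection or termination could be more frequent there.

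**Working it through.** **The plan's own figures.** The documents give no withdrawal or termination rate. Section 5.6 expects 432 evaluable from 432 enrolled. The related stated figures are the powers in 10.5, which reproduce with power = Φ(δ / (σ√(2/n)) − 1.96) and σ = 5 kg:

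- n = 200, δ = 2: Φ(4.00 − 1.96) = 97.9% (stated 97%)
- n = 200, δ = 1.75: Φ(3.50 − 1.96) = 93.8% (stated 93%)
- n = 160, δ = 2: Φ(3.58 − 1.96) = 94.7% (stated 94%)

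The 160-per-arm case in 10.5 is under-recruitment, not an allowance for withdrawal. No power loss is attributed to the withdrawal rule here.

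**Inputs for the illustration.**

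- From the documents: baseline HbA1c limits 5.4-6.4 (5.1); 12-month weight loss 2.5 kg (control) and 4.5 kg (intervention), SD 5 kg (10.5); 432/3 = 144 per arm.
- Assumed: baseline HbA1c mean 5.9, SD 0.25, truncated to those limits; 6-month change SD 0.25; one 6-month reading of 6.5 or more counts as diagnosis; correlation r between HbA1c change and weight change 0.3-0.5; HbA1c falls 0.05-0.15 more on intervention than on control.

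**Formula.** Let L be the proportion diagnosed in an arm, p the proportion of those terminated, and k their mean standardised HbA1c change. Diagnosed patients have on average r·5·k kg less weight loss than their arm's mean. Removing them raises the observed mean loss in that arm by p·L·r·5·k / (1 − p·L). The contrast moves by the intervention shift minus the control shift.

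**Worked case** (p = 1 in both arms, r = 0.5, no mean HbA1c change in control, 0.15 fall on intervention):

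- Control: L = 0.0354, k = 1.724. Shift = 0.0354 × 2.5 × 1.724 / 0.9646 = 0.158 kg.
- Intervention: L = 0.0112, k = 2.110. Shift = 0.0112 × 2.5 × 2.110 / 0.9888 = 0.060 kg.
- Observed contrast = 2.0 + 0.060 − 0.158 = 1.90 kg.

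**Ranges over the assumptions.**

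| Scenario | Diagnosed, control | Diagnosed, intervention | Observed contrast |
|---|---|---|---|
| (a) No control HbA1c change; all diagnosed terminated | 3.5% | 1.1-2.5% | 1.90-1.98 kg |
| (b) Control HbA1c falls 0.05-0.10; all diagnosed terminated | 1.7-2.5% | 0.5-1.7% | 1.92-1.99 kg |
| (c) As (a), but a quarter of diagnosed controls and all diagnosed intervention patients terminated | 3.5% | 1.1-2.5% | 2.01-2.08 kg |
| (d) As (a), but half of the diagnosed terminated in both arms, unweighted | 3.5% | 1.1-2.5% | 1.95-1.99 kg |

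In (a) the patients lost number about 5 of 144 in control (0.035 × 144) and 2-4 per 144 on intervention. Large simulations of the same scenarios agree to within 0.02 kg.

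**Scale.** SE = 5 × √(2/144) = 0.589 kg. The largest shift, 0.10 kg, is 0.10/0.589 = 0.17 SE.

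**What weighting can do.** In (d), weighting the retained diagnosed patients by 1/0.5 = 2 returns about 2.00 kg. In (a) and (b) no diagnosed patient is retained, so none can be up-weighted on diagnosis. Weighting therefore helps only if loss depends on recorded data, is not certain after diagnosis, and the weight model contains those data.

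**Other routes.** If lost participants differ from observed ones by s kg and the proportion lost differs by 10 points between arms, a simple comparison shifts by 0.10 × s: 0.2, 0.3 or 0.5 kg for s = 2, 3 or 5. With equal loss and equal s the shift is zero. These rates are assumed. Loss through new weight-changing conditions cannot be quantified from the documents.

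**The case against.** The strongest reply has four parts.

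First, termination is discretionary, and 5.7.1 limits it to a criterion that rules out further participation. Making diabetes a secondary endpoint suggests that incident cases are meant to be recorded, not removed. This stands as a limit on frequency: scenarios (a) and (b), where every diagnosed patient is terminated, are an upper bound. It does not close the route, because no section says that a new diagnosis leaves follow-up intact.

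Second, the planned analysis is weighted GEE with EHR supplementation, whereas (a)-(c) are unweighted observed-data contrasts. That is fair, and (d) shows that weighting can recover the effect. But 10.4.2 gives no weight model, and on a plain reading 5.7.2 stops the supplementation.

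Third, low app use is not defined as withdrawal, so disengaged participants stay in follow-up, and stopping collection is proper for someone who withdraws consent. Both points stand. What remains is participants who are terminated, or who leave the program or study contact, but would still allow outcome capture.

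Fourth, excluding weight after a new cancer or pregnancy may be a legitimate choice of estimand. It may be, but the plan does not state it and 10.3 points the other way. Collecting the values keeps either analysis possible.

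The Phase 3 consent form is a separate attachment and was not available, so it may already cover follow-up after discontinuation.

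**Conclusion.** The concern holds. Sections 5.7.2 and 7.3.5 state a rule that ends collection for every exit, including involuntary ones, while the ITT set remains all randomised participants and sources for later values already exist. One permitted reason for exit overlaps a secondary endpoint and another concerns conditions that move the primary endpoint.

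The likely size is modest: for the diabetes route, shifts of at most about 0.10 kg in a 2.0 kg difference, toward or away from no effect depending on which arm loses more. This rests on the assumed HbA1c distribution, correlation, diagnosis rule and termination proportions. Other routes could add to it but cannot be sized from the documents. The change should be made because the loss is avoidable and the remedy is cheap, not because the trial's conclusion is likely to turn on it.

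**What to change.** 1. In 5.7.2 and 7.3.5, state that, unless the participant withdraws consent or authorisation for further data use, scale weights and the planned EHR extraction of weight and HbA1c continue at 6 and 12 months after the program or study contact stops.
2. State that a diabetes diagnosis after randomisation, or a new condition under exclusion 2, does not by itself end outcome data collection. Which clinical termination rule applies is for the sponsor and investigator.
3. In 10.4.2, name recorded HbA1c, weight and diabetes diagnosis as variables in the weighted-GEE missingness model, and say that the EHR query covers participants who have left.
4. Record the reason for each withdrawal or termination, and report reasons by arm.
5. Reconcile sections 4.2.2, 5.2, 5.7.1, 5.7.2, 7.3.5 and 10.4.2.

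The cost is protocol and SAP wording, plus consent wording if the current form does not cover EHR extraction after discontinuation. The EHR query is already planned. Continued capture cannot apply once authorisation is revoked, since 13.5 then keeps only what was collected before. The change should be made while follow-up is open, because scale readings that were not collected may be unrecoverable later.
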